## **10. SUBJECT COMPLETION/WITHDRAWAL FROM THE STUDY**

### **10.1. Completion**

A subject will be considered to have completed the study if he or she has completed assessments at Month 24 of the assessment period (or until the last assessment, if the study is extended).

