**1. Since the last study site visit/telephone call, did the child have any wheezing?**

No → go straight to Section B

Yes ↓

- a. Please provide the days of wheezing and missing days of wheezing in the calendar below.

____/____ (Month/Year)						
Monday	Tuesday	Wednesday	Thursday	Friday	Saturday	Sunday

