2. GENERAL ANALYSIS DEFINITIONS

2.1. Visit Windows and Phase definition

As this is a LTFU of Study 64041575RSV2004, only 1 analysis phase will be defined (see [Table 1](#)). The reference is the date of informed consent in study 64041575RSV2002.

Table 1: Trial Phase

Trial Phase	Trial Phase (Numeric Version)	Start Date	End Date
Long Term Follow Up	1	00:00 of the date of signing the informed consent	Trial termination date (date of last contact) with timestamp 23:59

For assigning assessments, the visit schedule as reported in the database will be used.

If a subject has a missing visit, the data will be set to missing and will not be imputed. Information of an unscheduled visit will be merged with the scheduled visit, meaning that any information will be added to scheduled visit data.

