5. EFFICACY

5.1. Primary Efficacy Endpoint(s)

5.1.1. Definition

The primary endpoints are:

1. Clinical diagnosis of asthma within the first 2 years after the RSV infection, as diagnosed by a physician and reported by the parent/caregiver. This will be derived based on the completed study questionnaires at each visit/telephone call until the final visit. It is either “Yes” or “No”.
2. The percentage of wheezing days in a subject within the first 2 years after the RSV infection will be calculated as:

$$\text{Percentage of wheezing days} = \left(\frac{\text{number of wheezing days}}{\text{day of study completion} - \text{day of informed consent} + 1} \right) * 100$$

The percentage will be rounded to the nearest integer. Number of wheezing days is the sum of all days that were reported in the Monthly visit reports. The day of informed consent is the informed consent of the RSV2002 study.

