Incidence of reportable AEs and SAEs, including AEs related to respiratory illnesses and AEs considered at least possibly related to lumicitabine or placebo by the investigator.	These incidences are defined as the number of AEs overall and by category divided by the 2 year reporting period. Each AE is counted as reported. The unit will be ‘per month/during the first 2 years’. In case the subject did not report on the full 24 months the divisor will be adapted to nearest number of months participating.
Number of respiratory infections per subject during study participation	The total number of respiratory infections of each subject. The unit will be ‘during study participation’. The respiratory infection AE terms (AEDECOD) will be determined based on medical review and reported overall and by Preferred Term.
Medical resource utilization including the number of medical visits, emergency room visits, and hospitalizations, all for respiratory conditions only, based on information reported by the parent/caregiver.	Total number of medical visits, emergency room visits, and hospitalizations, as reported by the parent/caregiver. The number will be given overall and by relationship to respiratory conditions, as based on medical review.

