Impact of the subject's health problems on the parent's/caregiver's health per Month	The extent to which the subject's health problems impacted the parent's/caregiver's health per Month. The answer to Questionnaire section E question 4.
Inability of the parent/caregiver to care for other family members due to the subject's health per Month	The inability of the parent/caregiver to care for other family members due to the subject's health per Month. The answer to Questionnaire section E question 5. The result will be either "Yes" or "No".
Subject's health limited the parent's/caregiver's time spent with other family members each Month	The extent to which the subject's health limited the parent's/caregiver's time spent with other family members each Month.

	The answer to Questionnaire section E question 6. The result will be categorical as listed in the Questionnaire.
Percentage of days other family members missed from work due to the subject's health problems per Month	The percentage of days each Month that other family members missed from work due to the subject's health problems. Derived base on the Questionnaire section E question 7. Calculated as the number of days as recorded in question 7 divided by the number of days since the last study visit/telephone call. For subjects currently not in paid employment, the value will be 100% for parents/caregivers who were not employed due to the child's health problem and missing if this was not due the child's health problem.
Clinical diagnosis of eczema within the first 2 years after the RSV infection	Clinical diagnosis of eczema within the first 2 years after the RSV infection, as diagnosed by a physician and reported by the parent/caregiver. The result will be either "Yes" or "No". Derived based on the answer to Questionnaire section C until the Month 24 analysis visit.
Clinical diagnosis of allergic rhinitis within the first 2 years after the RSV infection	Clinical diagnosis of allergic rhinitis within the first 2 years after the RSV infection, as diagnosed by a physician and reported by the parent/caregiver. The result will be either "Yes" or "No". Derived based on the answer to Questionnaire section D until the Month 24 analysis visit.

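### The primary wheezing percentage divides by all calendar days, so days flagged missing or never covered by a report count as wheeze-free

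*SAP*

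**What the plan says.** **Formula.** In SAP 5.1.1 the numerator is defined by the sentence "Number of wheezing days is the sum of all days that were reported in the Monthly visit reports". The denominator is the day of study completion minus the day of RSV2002 consent, plus 1. The result is rounded to an integer. Neither term mentions days of unknown status.

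**Data collection.** Protocol Attachment 2, Section A, asks at each contact whether the child has wheezed since the previous one. After a Yes, the instruction is "Please provide the days of wheezing and missing days of wheezing in the calendar below". After a No, the interviewer is told to "go straight to Section B", so the calendar stays empty. The daily card (Attachment 3) is coded 1 or 0, and completed cards are kept in the study file.

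**Missing data.** SAP 2.1 leaves a missed visit missing, without imputation. SAP 5.2.1 drops the two imputations that Protocol 11.3.2 planned as sensitivity analyses.

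**Window.** SAP 2.1 defines one phase, from "00:00 of the date of signing the informed consent" to "Trial termination date (date of last contact) with timestamp 23:59". SAP 5.1.1 refers instead to study completion, which Protocol 10.1 defines as follows: "A subject will be considered to have completed the study if he or she has completed assessments at Month 24 of the assessment period" (or the last assessment if the study is extended). SAP 2.5 makes the Screening report the first report. Under Protocol 9.1.2 that report looks back either to the parent study's Day 14 visit or over at most 30 days.

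**Monthly version.** SAP Table 2 defines the numerator of the monthly wheezing percentage and names no denominator.

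**The concern.** An unknown day and a confirmed wheeze-free day enter the formula identically: 0 in the numerator and 1 in the denominator. Leaving missed visits unimputed does not prevent this, because the denominator is not reduced to match. The result is a silent imputation of no wheezing, although the questionnaire asks for missing days separately.

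This is one of two primary endpoints. A child who wheezed and has gaps in reporting gets a lower percentage than the reported days support, and with so few children one value can move a group mean. The summaries by treatment group would not show it.

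**Working it through.** The plan states no wheezing rate and no missing-day rate, so there is no figure to reproduce. The rates below are assumptions, shown over a range.

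**Inputs.** D = 731 days from consent to completion (assumed 730 days of follow-up, plus 1 from the formula). U = days of unknown status, W = reported wheezing days, m = U/D.

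**Step 1: SAP value against known-day value.** The SAP value is 100 × W/D and the known-day value is 100 × W/(D − U). Their ratio is (D − U)/D = 1 − m. For one lost 30-day report, m = 30/731 = 4.1%.

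| Known-day percentage (assumed) | 30 days unknown (4.1%) | 10% unknown | 20% unknown |
|---|---|---|---|
| 5% | 4.8 | 4.5 | 4.0 |
| 10% | 9.6 | 9.0 | 8.0 |
| 20% | 19.2 | 18.0 | 16.0 |

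**Step 2: rounding.** At 10%, the printed integer falls to 9 only when 10 × (1 − m) < 9.5, that is m > 5%. Since 0.05 × 731 = 36.55, at least 37 unknown days are needed. One lost 30-day report leaves the printed value at 10%.

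**Step 3: direction relative to the truth.** Assume 720 days, with 12 wheezing days in each of 6 thirty-day months and none in the other 18. The true value is 72/720 = 10.0%. Let 20% of all days be unknown.

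- If wheezing days are lost in proportion, 72 × 0.8 = 57.6 are reported and the SAP gives 57.6/720 = 8.0%, which is too low.
- If every wheezing day is reported and only quiet days are lost, the SAP gives 72/720 = 10.0%, which is correct. Removing all unknown days would give 72/576 = 12.5%, which is too high.

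**Step 4: what the questionnaire can correct.** Missing days are flagged only after a Yes, so at most 6 × 30 × 0.2 = 36 days can be removed.

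- Proportional loss: 57.6/(720 − 36) = 57.6/684 = 8.4%, against a true 10.0%.
- Only quiet days lost: 72/684 = 10.5%, against a true 10.0%.
- Reaching 57.6/576 = 10.0% under proportional loss needs a different, card-based rule that also treats blank card days in the No months as unknown.

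**Step 5: pre-consent days.** If days recalled at Screening were summed, they would enter the numerator only. The upper bounds are 14/731 = 1.9 points (recall from Day 14 to Day 28) and 30/731 = 4.1 points (30-day recall). Both require every recalled day to have had wheezing. With none, the effect is 0.

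**The case against.** The strongest case against is that little is at stake. There are 7 children, nothing is tested and the project has stopped. A missed call need not create unknown days, because the next contact asks about all the time since the last one. The listings promised in SAP 5.2.2 let a reader look for gaps child by child. The known-day denominator can also err, in the opposite direction, if quiet days are the ones left unrecorded. All of this stands and limits the severity. It does not change how the formula treats a day that is flagged missing or never reported.

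A reader might also infer more than the documents support:

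- **That the SAP already uses known-day divisors elsewhere.** For AE incidence it says "In case the subject did not report on the full 24 months the divisor will be adapted to nearest number of months participating", which is participation time. For family work days the count is "divided by the number of days since the last study visit/telephone call", and for the caregiver's own work days it is the length of the reported month. Both are full calendar intervals. None of the three removes unknown days.
- **That the window is open enough to halve a value.** For a child who leaves at 12 months with an assumed 36 wheezing days, 36/366 = 9.8% but 36/731 = 4.9%. The second figure needs a planned Month 24 date for a child who never reached it. The only trial end date that the SAP defines is last contact.
- **That pre-consent days inflate the endpoint by up to 4.1 points.** The SAP phase starts at consent, and the two-year episode count in Table 2 is limited to consent onward. What is missing is a cross-reference in SAP 5.1.1.
- **That many missed reports cut the value sharply.** Six or twelve missing reports would take 10% to 7.5% or 5.0%, but only if every missed report left its days permanently unknown.

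**Conclusion.** The point holds in a limited form. As written, SAP 5.1.1 scores days flagged missing or never covered by a report as wheeze-free. This lowers the percentage, relative to the known-day percentage, by the factor (1 − unknown share). The size is unknown because no missing-day rate is given: an assumed 10% falls to 9.0% or 8.0% with 10% or 20% of days unknown, and by less than rounding for one lost monthly report.

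It would be tempting to conclude that the endpoint understates true wheezing. That follows only if some unknown days had wheezing, which the documents do not show. The window is largely settled by SAP 2.1 and needs only to be stated in SAP 5.1.1. The consequence is confined to descriptive estimates and confidence intervals. Severity: minor to moderate.

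**What to change.** In SAP 5.1.1:

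1. Count wheezing days and denominator days over the same window, the SAP 2.1 phase: consent to date of last contact, including for children who discontinue. Exclude pre-consent recalled days from the numerator.
2. Divide by days covered by a completed report minus days flagged missing, with a No answer covering its whole interval.
3. Show the number of known-status days per subject beside the percentage.

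In SAP Table 2, state the same denominator for the monthly percentage.

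The cost is SAP wording and a small programming change. The documents do not say whether the missing-day flags from the paper questionnaire were entered in the database, so this should be checked first.

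The correction is partial (8.0% to 8.4% in the worked example, not 10.0%). It can overstate if quiet days are more often left unrecorded, and values will be noisier for children with few observed days. Using the returned cards to fill blank days is an optional check; it may mean extra data entry for 7 children.

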5.1.2. Estimand

The incidence of asthma will be evaluated descriptively as the difference in proportions of subjects with clinical diagnosis within the first 2 years after the RSV infection for the lumicitabine versus the placebo treatment.

5.1.3. Analysis Methods

The proportions of subjects with clinical diagnosis of asthma within the first 2 years after the RSV infection will be presented descriptively by previous treatment group, together with the 95% (2-sided) confidence intervals using the Wilson method.

The percentage of days with wheezing within the first 2 years after the RSV infection will be presented descriptively by previous treatment group, including 95% CIs.

5.2. Major Secondary Endpoints

5.2.1. Definition

The definitions of these endpoints are given in [Table 2](#). While the clinical trial protocol mentions two methods for imputing missing data, these methods will not be performed as based on the limited number of subjects enrolled in the study these analyses would not be meaningful.

Consecutive wheezing episodes will be combined.

Step 1: Combination of wheezing episodes

Consecutive wheezing episodes are defined as episodes of the same subject with the start date of an episode is exactly 1 day after the end date of the preceding episode (or same date). Wheezing

episodes can only be combined into one and the same episode if the start and stop dates are complete.

Step 2: Allocation of wheezing episodes to intervals. For analysis of incidence over time the wheezing episodes will be allocated into the analysis visits (intervals), using the start date of the episode. For the analysis of prevalence over time, the wheezing episodes will be counted in each interval it overlaps, using the available start and end date information.

Table 2: Calculations (Secondary Endpoints)

Parameter	Definition
Percentage of wheezing days per month	Percentage of wheezing days per month as based on Visit variable in the database using information reported by the parent/caregiver. The nominator is the number of Days reported in that period with wheezing, using last day – first day + 1 for reported days of wheezing. The fraction is multiplied by 100% and rounded to the nearest integer.
Number of wheezing episodes per month	Number of wheezing episodes during each month, after combination of the consecutive episodes, as based on information reported by the parent/caregiver. A wheezing episode is defined as the presence of wheezing for ≥ 1 day that started during the episode. If an episode is present but started in the previous episode it will not be counted.
Number of wheezing episodes within the first 2 years after the RSV infection	Number of wheezing episodes recorded between informed consent and the last day in the trial for completed subjects. It is the sum of the number of wheezing episodes across Months.
Incidence of reportable AEs and SAEs, including AEs related to respiratory illnesses and AEs considered at least possibly related to lumicitabine or placebo by the investigator.	These incidences are defined as the number of AEs overall and by category divided by the 2 year reporting period. Each AE is counted as reported. The unit will be ‘per month/during the first 2 years’. In case the subject did not report on the full 24 months the divisor will be adapted to nearest number of months participating.
Number of respiratory infections per subject during study participation	The total number of respiratory infections of each subject. The unit will be ‘during study participation’. The respiratory infection AE terms (AEDECOD) will be determined based on medical review and reported overall and by Preferred Term.
Medical resource utilization including the number of medical visits, emergency room visits, and hospitalizations, all for respiratory conditions only, based on information reported by the parent/caregiver.	Total number of medical visits, emergency room visits, and hospitalizations, as reported by the parent/caregiver. The number will be given overall and by relationship to respiratory conditions, as based on medical review.

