## 10.2. Withdrawal From the Study

A subject will be automatically withdrawn from the study for any of the following reasons:

- Lost to follow-up.
- Withdrawal of consent.
- Death.

If a subject is lost to follow-up, every reasonable effort must be made by the study site personnel to contact the parent/caregiver and determine the reason for withdrawal. The measures taken to follow up must be documented.

When a subject is withdrawn by his/her parent(s)/caregiver(s) before completing the study, the reason for withdrawal is to be documented in the eCRF and in the source document.

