**12.2. Procedures****12.2.1. All Adverse Events**

All reportable AEs and SAEs will be reported from the time a signed and dated ICF is obtained until completion of the subject's last study-related procedure, which may include contact for

follow-up of safety. SAEs, including those spontaneously reported to the investigator, must be reported using the SAE Form.

All events that meet the definition of an SAE will be reported as SAEs.

All SAEs and reportable AEs must be recorded using medical terminology in the source document and the eCRF. Whenever possible, diagnoses should be given when signs and symptoms are due to a common etiology (eg, cough, runny nose, sneezing, sore throat, and head congestion should be reported as “upper respiratory infection”). Investigators must record in the eCRF their opinion concerning the relationship of the AE to the study drug administered in Study 64041575RSV2004. All measures required for AE management must be recorded in the source document and reported according to sponsor instructions.

The sponsor assumes responsibility for appropriate reporting of AEs to the regulatory authorities. The sponsor will also report to the investigator (and the head of the investigational institute where required) all SUSARs. The investigator (or sponsor where required) must report SUSARs to the appropriate Independent Ethics Committee/Institutional Review Board (IEC/IRB) that approved the protocol unless otherwise required and documented by the IEC/IRB.

For all studies with an outpatient phase, including open-label studies, the subject’s parent/caregiver must be provided with a “wallet (study) card” and instructed to carry this card with them for the duration of the study indicating the following:

- Study number.
- Statement, in the local language(s), that the subject is participating in a clinical study.
- Investigator’s name and 24-hour contact telephone number.
- Local sponsor’s name and 24-hour contact telephone number (for medical personnel only).
- Site number.
- Subject number.

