1.3. Statistical Hypotheses for Trial Objectives

No formal hypothesis testing will be performed. The hypothesis to be explored is that treatment of RSV-infected infants and children with lumicitabine will decrease the incidence of subsequent asthma and/or wheezing compared with infants and children treated with placebo.

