2.4. Definition of Subgroups and Subsets

As study 64041575RSV2002 only included 7 subjects, no subgroups or subsets will be defined.

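### The AE incidence in SAP Table 2 divides by follow-up rounded to the nearest month, with no minimum, no defined month and no group-rate rule; exact child-days would be better

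*SAP*

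**What the plan says.** The incidence of reportable AEs and SAEs is a secondary endpoint in Protocol 2.1.2, and SAP 5.2.1, Table 2, gives its formula: "These incidences are defined as the number of AEs overall and by category divided by the 2 year reporting period". Each event counts as reported, so repeat events all enter the numerator. The unit is given both per month and over the first two years.

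For incomplete follow-up, Table 2 adds: "In case the subject did not report on the full 24 months the divisor will be adapted to nearest number of months participating". The adjustment is therefore made child by child. SAP 5.2.2 sets out methods for wheezing and respiratory infections but none for this rate.

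Four other places bear on the point:

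- **Dates.** Protocol 12.2.1 starts collection at consent: "All reportable AEs and SAEs will be reported from the time a signed and dated ICF is obtained". SAP 2.1, Table 1, ends the single analysis phase at the "Trial termination date (date of last contact) with timestamp 23:59". Exact days of follow-up are therefore available.
- **Practice elsewhere in the SAP.** The primary wheezing percentage (SAP 5.1.1) divides by days from consent to completion. Only the resulting percentage is rounded, not the divisor.
- **Early exit.** Protocol 10.2 says "A subject will be automatically withdrawn from the study for any of the following reasons", then lists loss to follow-up, withdrawal of consent and death. It sets no minimum stay.
- **Size and purpose.** SAP 2.4: "As study 64041575RSV2002 only included 7 subjects, no subgroups or subsets will be defined". SAP 1.3: "No formal hypothesis testing will be performed".

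**The concern.** Rounding the divisor of a rate does little harm when follow-up is long and a great deal when it is short. The clause exists only for children with incomplete follow-up, which includes the short stays where it behaves worst. A stay under half a month can round to zero and leave no rate at all. Stays of 16 days and 45 days can share the same divisor.

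At stake is the reported AE rate for an early leaver. If per-child rates were listed or averaged, a group figure in a study of 7 children would also be affected. Because the SAP does not say how the group rate is formed, two programmers could produce different figures from the same data.

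**Working it through.** The plan states no rate or precision for this endpoint, so there is no figure of its own to reproduce. The check below asks how far the rounding rule can move the rate.

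**Inputs.** Follow-up is *d* days from consent to last contact (Protocol 12.2.1; SAP 2.1). The SAP divisor is *d*/*M* rounded to the nearest whole number (Table 2; whole is the natural reading, though the SAP does not use the word). Month length *M* = 365.25/12 = 30.4375 days is an assumption.

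**Formula.** The reported rate is AEs / round(*d*/*M*), and the rate on exact time is AEs / (*d*/*M*). The relative error is therefore (*d*/*M*) / round(*d*/*M*) − 1, whatever the AE count, provided it is not zero.

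**Single days.**

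| Day | Exact months | Divisor | Error in rate |
|---|---|---|---|
| 15 | 0.493 | 0 | undefined |
| 16 | 0.526 | 1 | −47.4% |
| 45 | 1.478 | 1 | +47.8% |
| 46 | 1.511 | 2 | −24.4% |
| 76 | 2.497 | 2 | +24.8% |

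**Range of error by length of stay.**

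| Days followed | Lowest | Highest |
|---|---|---|
| 1–15 | undefined | undefined |
| 16–45 | −47.4% | +47.8% |
| 46–76 | −24.4% | +24.8% |
| 77–106 | −15.7% | +16.1% |
| 107–182 | −12.1% | +11.7% |
| 183–365 | −7.1% | +7.9% |
| 366–730 | −3.7% | +4.0% |

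**Sensitivity to the month.** With *M* = 28, 30 or 31 days, and ties rounded up or to even, the zero divisor lasts through day 13 to 15. The worst overstatement is 46.4% to 48.4% and the worst understatement 46.4% to 50.0%. The largest error is 8.3% over days 183–365 and 4.2% in the second year.

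**If events and time are pooled.** Take seven children, six followed for 24 months (6 × 24 = 144 months) and one early leaver:

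- Leaves on day 15: (144 + 0.493)/(144 + 0) − 1 = +0.34%.
- Leaves on day 16: (144 + 0.526)/(144 + 1) − 1 = −0.33%.
- Leaves on day 45: (144 + 1.478)/(144 + 1) − 1 = +0.33%.

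The documents do not give the split by treatment. In an assumed group of two, one completer and one leaver on day 45, the error is (24 + 1.478)/(24 + 1) − 1 = +1.9%. Pooling therefore removes most of the problem even in a very small group.

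**The case against.** The strongest reply is that little depends on this rate. The study is descriptive. Protocol 11.5 summarises AEs as the percentage of subjects with at least one occurrence. SAP 6.1.2 reports numbers of subjects with events, numbers of events per subject, a table by system organ class and preferred term, and listings of all reportable AEs. None of these uses the divisor, so no event can be lost or distorted through it. This stands, and it is why the point is minor.

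The second reply is that the zero divisor depends on how months are counted. SAP 2.5 builds its monthly schedule from successive reports: the first is Screening, the next is Month 2, and the numbering reflects time since the RSV event. On that reading, months participating could be a count of reports, and a child with only the entry report need not get a divisor of zero. This also stands. It makes the undefined rate conditional, and it shows that the clause admits two readings.

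Two stronger readings should be resisted.

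- **A group rate inflated almost threefold.** A reader might take four children with 2 AEs each in 24 months and a fifth with 1 AE in 1 month. Averaging per-child rates per 24 months gives (24 + 2 + 2 + 2 + 2)/5 = 6.4, against a pooled 24 × 9/97 = 2.2. Every stay in that example is a whole number of months, so rounding contributes nothing. The gap comes from averaging per-child rates, which the SAP never says it will do. The example shows only that the choice of group summary needs stating.
- **An early leaver actually distorting this study.** The documents give no dropout times and no group sizes, only the total of 7.

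**Conclusion.** The point holds as a minor flaw in a stated definition. Table 2 rounds follow-up where exact dates are available, sets no floor, and omits both the meaning of a month and the rule for a group rate.

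On elapsed months of about 30.4 days, a per-child rate is undefined through day 15 and at worst about 48% wrong at 16 to 45 days of follow-up. The error fades quickly as follow-up lengthens, and pooling makes it negligible. These sizes rest on the assumed month, on elapsed rather than report-counted time, and on rounding to whole months.

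Whether the rule affects any child in this study cannot be told from the documents. No test or decision described in them depends on the rate. The reason to change it is that exact time is free, unambiguous and already the SAP's practice for its primary wheezing endpoint.

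**What to change.** In SAP 5.2.1, Table 2, delete the sentence that adapts the divisor to the nearest number of months. Define the incidence for each previous treatment group, overall and by category, as

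(total reportable AEs ÷ total child-days) × days in 24 months,

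where child-days run from consent in Study 64041575RSV2002 to the date of last contact, counted inclusively, and 24 months is fixed as 24 × 30.4375 = 730.5 days. Choose this one scale in place of the two units now given. List each child's event count and days of follow-up beside the rate, so that a short stay is visible.

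The cost is a few words in the SAP and one line of code. No new data are needed, and the other AE tables are unchanged.
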